## 5.0 Consent Process and Documentation

### 5.1 Consent Process

**Check all that apply:**

**Informed consent will not be obtained – request to completely waive or alter the informed consent requirement. [Complete Section 5.1.1]**  
[Review the "CHECKLIST: Waiver or Alteration of Consent Process (HRP-410)" to ensure you have provided sufficient information for the IRB to make these determinations. HRP-410 can be accessed by clicking the IRB Library link in CATS IRB (<http://irb.psu.edu>). Waiver of consent is the most frequently requested type of consent for both retrospective and prospective chart reviews and existing restricted data sets.]

**Informed consent will be sought and documented with a written consent form [Complete Sections 5.1.2, 5.2.1 and 5.3 (when 5.3 is applicable)]**  
[Review "SOP: Written Documentation of Consent (HRP-091)" for information about the process to document the informed consent process in writing. HRP-091 can be accessed by clicking the IRB Library link in CATS IRB (<http://irb.psu.edu>.)]

**Implied or verbal consent will be obtained – subjects will not sign a consent form [Complete Sections 5.1.2, 5.2.2 and 5.3 (when 5.3 is applicable)]**  
[Review "CHECKLIST: Waiver of Written Documentation of Consent (HRP-411)" to ensure that you have provided sufficient information. HRP-411 can be accessed by clicking the IRB Library link in CATS IRB (<http://irb.psu.edu>). If your research presents no more than minimal risk of harm to subjects and involves no procedures for which written documentation of consent is normally required outside of the research context, the IRB will generally waive the requirement to obtain written documentation of consent.]

### **5.1.1 Waiver or alteration of the informed consent requirement**

The research poses no more than minimal harm to subject (i.e., loss of confidentiality/privacy). The waiver will not adversely affect the rights and welfare of subjects because the research results will not affect the care of the subjects. Given the number of subjects and the possibility that subjects may no longer be living or lost to follow-up, this research would not be practical without this waiver. No information which would be pertinent to the on-going care of individual subjects is expected to result from this study.

### **5.1.2 Obtaining Informed Consent**

N/A

## **5.2 Consent Documentation**

### **5.2.1 Written Documentation of Consent**

N/A

### **5.2.2 Waiver of Documentation of Consent (Implied consent, Verbal consent, etc.)**

The proposed research presents no more than minimal risk of harm to subjects and involves no procedures for which written documentation of consent is normally required outside of the research context.

## **5.3 Consent – Other Considerations**

### **5.3.1 Non-English Speaking Subjects**

N/A

### **5.3.2 Cognitively Impaired Adults**

N/A

#### **5.3.2.1 Capability of Providing Consent**

N/A

#### **5.3.2.2 Adults Unable To Consent**

N/A

#### **5.3.2.3 Assent of Adults Unable to Consent**

N/A

### **5.3.3 Subjects who are not yet adults (infants, children, teenagers)**

#### **5.3.3.1 Parental Permission**

N/A

### 5.3.3.2 Assent of subjects who are not yet adults

N/A

## 6.0 HIPAA Research Authorization and/or Waiver or Alteration of Authorization

### 6.1 Authorization and/or Waiver or Alteration of Authorization for the Uses and Disclosures of PHI

Check all that apply:

- Not applicable, no identifiable protected health information (PHI) is accessed, used or disclosed in this study. [Mark all parts of sections 6.2 and 6.3 as not applicable]
- Authorization will be obtained and documented as part of the consent process. [If this is the only box checked, mark all parts of sections 6.2 and 6.3 as not applicable]
- Partial waiver is requested for recruitment purposes only (Check this box if patients' medical records will be accessed to determine eligibility before consent/authorization has been obtained). [Complete all parts of sections 6.2 and 6.3]
- Full waiver is requested for entire research study (e.g., medical record review studies). [Complete all parts of sections 6.2 and 6.3]
- Alteration is requested to waive requirement for written documentation of authorization (verbal authorization will be obtained). [Complete all parts of sections 6.2 and 6.3]

### 6.2 Waiver or Alteration of Authorization for the Uses and Disclosures of PHI

#### 6.2.1 Access, use or disclosure of PHI representing no more than a minimal risk to the privacy of the individual

##### 6.2.1.1 Plan to protect PHI from improper use or disclosure

Information is included in the "Confidentiality, Privacy and Data Management" section of this protocol.

##### 6.2.1.2 Plan to destroy identifiers or a justification for retaining identifiers

Data will be de-identified.

#### 6.2.2 Explanation for why the research could not be practically conducted without access to and use of PHI

Retrieval of study data necessitates access to patient charts through their MRNs. Once this information is obtained, it will be identified with code numbers linked to patient MRN's

#### 6.2.3 Explanation for why the research could not practically be conducted without the waiver or alteration of authorization

Given the number of subjects and the possibility that subjects may no longer be living or have current contact information, this research would not be practical without waiver. No clinical information which would be pertinent to the care of individual subjects is expected to result from this study

#### 6.2.4 Waiver or alteration of authorization statements of agreement

Protected health information obtained as part of this research will not be reused or disclosed to any other person or entity, except as required by law, for authorized oversight of the research study, or for other permitted uses and disclosures according to federal regulations. The research team will collect only information essential to the study and in accord with the 'Minimum Necessary' standard (information reasonably necessary to accomplish the objectives of the research) per federal regulations. Access to the information will be limited, to the greatest extent possible, within the research team. All disclosures or releases of identifiable information granted under this waiver will be accounted for and documented.

## 7.0 Study Design and Procedures

### 7.1 Study Design

Check all that apply:

**Analysis of an existing restricted data set.** Existing means that all of the data to be used in this study are already in existence when the study is initially submitted to this IRB for review.

**Retrospective chart/record review** – A retrospective chart/record review study means that all of the data to be used in this study are already in existence when the project is initially submitted to this IRB for review.\*

\*Provide date range of chart/record review (mm/dd/yyyy to mm/dd/yyyy):  
2009-2019

**Prospective chart/record review** – A prospective chart/record review study means that all of the data are not in existence when the project is initially submitted to this IRB for review.

### 7.2 Study Procedures

For the specific needs of this proposal, we will define 2 patient cohorts using the PaTH Network: (1) Diabetes cohort and (2) At-risk for diabetes cohort. As demonstrated in the table below, there are over 328,000 patients with a diagnosis of diabetes (defined as age 18 and older with a diagnosis of diabetes mellitus – ICD9 250.xx) and over 2 million patients at risk for diabetes (defined as age 18 and older with a BMI of  $\geq 25$ ) within the PaTH network.

Patient Characteristics	Penn State University (N=25,219)	University of Pittsburgh (N=150,589)	Johns Hopkins University (N=60,324)	Temple University (N=40,536)	University of Utah (N=51,787)	PaTH Total (N=328,455)
Patients with Diabetes						
Insurance type						
Private	9,874 (38%)	60,223 (40%)	32,371 (54%)	5,261 (13%)	21,264 (41%)	128,993 (39%)
Medicaid	1,890 (8%)	10,165 (7%)	727 (1%)	21,759 (54%)	4,189 (8%)	38,730 (12%)
Medicare	12,998 (52%)	54,675 (36%)	22,826 (38%)	10,916 (27%)	23,997 (46%)	125,412 (38%)
Uninsured	457 (2%)	11,625 (8%)	485 (1%)	2,599 (6%)	2,337 (5%)	17,503 (5%)
Race						
White	21,780 (86%)	116,056 (77%)	32,544 (54%)	14,347 (35%)	39,580 (76%)	224,307 (68%)
African-American	1,679 (7%)	15,336 (10%)	20,053 (33%)	14,656 (36%)	944 (2%)	52,668 (16%)
Other	1,760 (7%)	19,197 (13%)	7,727 (13%)	11,533 (29%)	11,263 (22%)	51,480 (16%)
Hispanic Ethnicity	1,054 (4%)	697 (0.5%)	2,002 (3%)	7,356 (18%)	6,077 (12%)	17,186 (5%)
Female Gender	12,014 (48%)	70,623 (47%)	30,912 (51%)	22,485 (55%)	25,727 (50%)	161,761 (49%)
Patients At-Risk for Diabetes						
	(N=167,799)	(N=950,020)	(N=471,860)	(N=212,314)	(N=260,506)	(N=2,062,499)
BMI						
25-29.9	69,353 (30%)	433,799 (31%)	226,113 (32%)	92,807 (31%)	122,583 (31%)	944,655 (32%)
30-34.9	48,353 (21%)	268,236 (19%)	128,799 (18%)	60,330 (20%)	87,023 (22%)	592,741 (20%)
35-39.9	25,388 (11%)	128,113 (9%)	58,072 (8%)	29,930 (10%)	70,774 (18%)	312,277 (10%)
40+	24,705 (11%)	94,550 (7%)	43,377 (6%)	23,321 (8%)	25,410 (7%)	211,363 (7%)

***Diabetes Cohort Definition.*** During year 1 of the proposed project, the investigative team, in collaboration with the PaTH Network, will identify a valid cohort of patients with type 2 diabetes. The cohort of patients under study will be defined as all patients age 18 and older with an indication of type 2 diabetes during the proposed study time frame. Patients will be classified as having diabetes using a clinically validated algorithm: type 2 diabetes mellitus on the problem list, diabetes-specific medications, hemoglobin A1c (HbA1c) results > 7.0%, or one inpatient diagnosis code or two outpatient diagnosis codes for type 2 diabetes (ICD-9 codes 250.xx). The diabetes cohort will be further limited to patients who will likely be captured in the PaTH EHR records or claims data so that outcome assessments can occur. Thus, we will further limit the diabetes cohort to patients who have either: (1) had at least 2 outpatient primary care visits in one of the PaTH health systems in the past 3 years (since January 1, 2012), or (2) for whom claims data are available. The cohort will be dynamic, with new patients added into the cohort after 2015 as they meet the diabetes cohort definition prospectively. The observational period for the outcome variables will be for the 10-year period from 2009-2019, thus including 3 years of data prior to the first policy change (CMS instituting coverage for intensive behavioral therapy for obesity) and 3 years after the last policy change (Pennsylvania Medicaid expansion) under study.

Following the definition of the diabetes cohort and key diabetes outcomes and covariates as described above, an initial extraction of variables will be conducted in Year 2 of the proposed project for years 2009-2015. This early data extraction from the PaTH Network will allow for cohort validation and data cleaning and editing, as well as required programming and determination of the analysis models. We will utilize this initial data extraction in Years 2 and 3 to analyze the impact of early health policy changes, as well as to prepare a manuscript of both the protocol and early findings of policy impact. The final data extraction will occur during the final quarter of Year 4 of the proposed project, allowing for completion of a ten-year time period (2019).

***At-risk Cohort Definition.*** The cohort of patients under study will be defined as patients age 18 and older who are at risk for the development of diabetes, based on being overweight. Patients seen at one of the four PaTH institutions will be included in the at-risk cohort if they have a  $BMI \geq 25 \text{ kg/m}^2$ , based on most recent recorded weight and at least one recorded height. The at-risk cohort will be further limited to patients who will likely to be captured in the PaTH EHR records or claims data so that outcome assessments can occur. Thus, we will further limit the at-risk cohort to patients who have either: (1) had at least 2 outpatient primary care visits in one of the PaTH health systems in the past 3 years (since January 1, 2012), or (2) for whom claims data is available. The cohort will be dynamic, with new patients added into the cohort after 2015 as they meet the at-risk cohort definition prospectively. Patients will not be removed from the cohort, even if they are no longer overweight. The observational period for the outcome variables will be for the 10-year period from 2009-2019, thus including 3 years of data prior to the first policy change (CMS instituting coverage for intensive behavioral therapy for obesity) and 3 years after the last policy change (Pennsylvania Medicaid expansion) under study.

[figure not shown]
intensive behavioral therapy for obesity) and 3 years after the last policy change (Pennsylvania Medicaid expansion) under study.

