## **3.0 Inclusion and Exclusion Criteria**

### **3.1 Inclusion Criteria**

#### **Patients with Diabetes**

- Ages 18 and older
- Indication of Type 2 Diabetes as defined using a clinically validated algorithm: type 2 diabetes mellitus on the problem list, diabetes-specific medications, hemoglobin A1c (HbA1c) results > 7.0%, or one inpatient diagnosis code or two out-patient diagnosis codes for type 2 diabetes (ICD-9 codes 250.xx)
- patients who have either: (1) had at least 2 outpatient primary care visits in one of the PaTH health systems in the past 3 years (since January 1, 2012), or (2) for whom claims data are available

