To evaluate the impact of policy changes on these outcomes, we will examine how these outcomes change over time, in response to the policy changes. As descriptive analyses, we will plot the mean trajectory of each yearly outcome at clinic level, health system level and state level. The statistical modeling of patterns of changes in individual level outcomes will be carried out through multi-level mixed-effects models. The mixed-effects model is a common and popular modeling technique for longitudinal data. A mixed-effects model can accommodate within- and between-subjects variability, as well as serial correlations. In addition, it has the flexibility to incorporate time-dependent covariates, incomplete data, and heteroscedasticity of the variances and correlations. The mixed-effects model will be specified in a multi-level fashion so that different levels of variability (e.g., individual characteristics, social environment, built environment) can be taken into account. The pattern of changes in the outcome will be assessed for pre- and post-periods, respectively, based on the piecewise/segmented regression models. The slope of each segment indicates the trend of change in diabetes outcome in that period. Therefore, the change in the trend/slope post-policy implementation may reveal the actual impact of the new policy controlling for baseline level and trend. Such modeling strategies share the same spirit of interrupted time series analysis. While the classical interrupted time series design often generates a single long series of data, we have a large number of short series from each individual subject, namely, longitudinal data. Depending on the types of the outcomes, we will specify mixed-effects models based on logistic

regression for a binary outcome, Poisson regression for a count outcome and linear regression for a continuous outcome as detailed below.

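### No rule starts a patient's diabetes person-time at the first indication of diabetes, so years before onset can enter the pre-policy trend and bias the slope change

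*Combined protocol and SAP*

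**What the plan says.** Protocol Section 7.2 (Diabetes Cohort Definition) admits "all patients age 18 and older with an indication of type 2 diabetes during the proposed study time frame". For that cohort, "The observational period for the outcome variables will be for the 10-year period from 2009-2019".

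Capture is by one of two routes, also listed in Section 3.1. The patient must have "had at least 2 outpatient primary care visits in one of the PaTH health systems in the past 3 years (since January 1, 2012"), or be someone "for whom claims data are available". The first route carries a date; the second does not.

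On later entry, Section 7.2 says: "The cohort will be dynamic, with new patients added into the cohort after 2015 as they meet the diabetes cohort definition prospectively". It also says that, once the cohort and outcomes have been defined, "an initial extraction of variables will be conducted in Year 2 of the proposed project for years 2009-2015".

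Section 8.0 models each subject's yearly outcomes from five years before the policy to five years after. Its only allowance for fewer time points is that a subject may be absent from the health system in some years. The policy effect is read as follows: "the change in the trend/slope post-policy implementation may reveal the actual impact of the new policy controlling for baseline level and trend".

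Table 1 in Section 7.2 scores a year without an A1c as uncontrolled diabetes. It defines diabetes service use by visits and admissions that carry a diabetes diagnosis.

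**The concern.** Membership is decided by information that may come after the outcome year. A patient whose first indication falls in 2014 belongs to the cohort, and the text gives no reason to leave out that patient's 2009-2013 outcomes. In those years the patient had not met the definition.

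Several Table 1 outcomes can be expected to shift at onset. Visits with a diabetes diagnosis are close to absent beforehand by construction. The control outcome depends on how often an A1c is measured before onset, because an unmeasured year counts as uncontrolled. Among patients back-filled in this way, the share of pre-onset years is largest in 2009 and shrinks each year. That gives the pre-policy segment a slope unrelated to any change in care, and the planned estimand is a difference from that slope.

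A second, narrower issue is the visit route's date condition, "in the past 3 years (since January 1, 2012"). For patients who enter that way, 2009-2011 data come only from people still in care in 2012 or later.

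**Working it through.** **Plan's own figures.** The five site counts in Section 7.2 add up: 25,219 + 150,589 + 60,324 + 40,536 + 51,787 = 328,455. This is a count by diagnosis code. It does not show how many patients already had diabetes in 2009. The years 2009-2019 give 11 annual points, matching t = -5 to 5 around 2014 in Section 8.0.

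**Calendar check, visit route.** The years 2009, 2010 and 2011 precede 1 January 2012. They are 3 of 3 pre-policy years with a 2012 origin, 3 of 4 with 2013 and 3 of 5 with 2014.

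**Assumed inputs (none is in the documents).** Share of the cohort with onset after 2009, inc = 10-40%. Probability that a pre-onset year scores uncontrolled, u = 50-90%, with 10% as a contrast. Probability after onset, 23.5%, constant, so there is no real change and no policy effect. Break at 2013, the year Section 2.1 gives for universal insurer coverage. Onsets spread evenly up to a last year L.

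**Formulas.**
- Pre-onset share in year y: s(y) = inc × (L − y)/(L − 2009), and 0 after L.
- Measured uncontrolled: U(y) = s(y) × u + (1 − s(y)) × 0.235.
- Two-segment logistic fit to 1 − U(y), as in Section 8.0 but fixed effects only, equal weight per year; b1 before and b2 after the break. False slope change = b2 − b1, in log odds of control per year.

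**Worked case (inc = 40%, u = 90%, L = 2015).**
- 2009: 0.40 × 0.90 + 0.60 × 0.235 = 0.501.
- 2013: s = 0.40 × 2/6 = 0.133, so U = 0.133 × 0.90 + 0.867 × 0.235 = 0.324.
- 2015 onwards: 0.235.
- Fit to 2019: b1 = +0.221, b2 = +0.077, difference −0.143.

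At the low end (inc = 10%, u = 50%), the 2009 value is 0.10 × 0.50 + 0.90 × 0.235 = 0.262.

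**Results.**

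| Scenario | Low end | High end |
|---|---|---|
| Onsets to 2015, fit 2009-2019 | −0.020 | −0.143 |
| Onsets to 2015, fit 2009-2015 only | +0.001 | +0.040 |
| Onsets spread to 2019, fit 2009-2019 | +0.001 | +0.019 |
| As first row, but u = 10% | +0.011 | +0.050 |

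The low end is inc = 10% and the high end 40%; in the first three rows u is 50% and 90% respectively. In the third row the slope change nearly cancels, but both slopes are wrong: b1 is +0.014 to +0.105 and b2 is +0.014 to +0.124, where the truth is zero.

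**With person-time starting at first indication**, s(y) = 0 throughout, U(y) = 0.235 every year, and both slopes and their difference are zero.

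**Service use.** Assume no diabetes-coded visits before first indication and a constant rate after it, so the mean rate is proportional to 1 − s(y). With onsets to 2015, a fit to 2019 and the same break, a Poisson fit gives a false pre-policy rise of 0.021-0.105 log rate per year and a false slope change of −0.016 to −0.084. In the other two onset and fit settings the slope change is about −0.001 to −0.02.

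**The case against.** The best defence is that the protocol is silent rather than wrong. It sets a period for the outcomes, not a start for each patient; it calls the cohort dynamic; and its diabetes-incidence outcome requires dating onset anyway. This stands for patients added after 2015: the text says they enter prospectively and leaves open whether their earlier years are used. It does not stand for those who first qualify in 2010-2015. For them the definition, the outcome period, the 2009-2015 extraction and the model's only limit on years all point to back-filling. Subject-specific slopes do not help, because the subject's own series contains the pre-onset years. The subgroup of patients newly enrolled in the system is not a subgroup of new diabetes, and onset date is not among the listed propensity-score inputs.

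A reader might infer three stronger things that the documents do not support.

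- **All pre-policy data come from survivors to 2012.** The claims route has no date, so this holds for the visit route only.
- **The plan will produce a false slope change of known direction.** The table shows either sign. The negative range for control needs onsets that end in 2015, a fit to 2019 and frequent uncontrolled scoring before onset. The documents give neither the incident share nor the pre-onset A1c testing rate.
- **The bias can be set against a sampling error for 328,455 independent patients.** Section 8.0 specifies subject and cluster random effects, so that contrast would be overstated.

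The scope is also limited. The post-policy counseling analysis in Section 8.0 does not use the pre-policy trend, and the counseling probability and weight loss between counseling visits do not depend on the A1c rule.

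**Conclusion.** The concern holds for the segmented pre/post analysis of diabetes outcomes. As written, patients first qualifying in 2010-2015 supply years before they met the definition. This biases the pre-policy slope whenever the outcome differs before and after onset, and it can bias the slope change. For patients added after 2015 the rule is unspecified rather than wrong. The selection on later care applies to visit-route patients only.

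Size and sign are undetermined. Under the stated assumptions the false slope change in control runs from about −0.14 to +0.05 log odds per year, a ratio of annual odds ratios of 0.87 to 1.05. It depends on the incident share, the timing of onsets, the fitted years and how often pre-onset years score as uncontrolled. It vanishes if outcomes are the same before and after onset. Section 8.0 expects power for very small effects, so sample size will not remove such an artefact and may make it statistically significant.

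**What to change.** Before extraction, define an index date as the date on which the diabetes algorithm is first satisfied, and count diabetes-outcome person-years only from then on. State that the same rule covers patients added after 2015. Add a sensitivity analysis restricted to patients who already met the definition and were in care at the start of the study period.

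Replace the fixed since-2012 visit condition with a year-by-year look-back only if records before 2009 are available. Section 7.1 starts the records in 2009, so a full three-year look-back is first possible for 2012. Without earlier records, visit-route patients would lose 2009-2011, the very years meant to precede the first policy change. In that case keep the visit rule and report the selection as a limitation.

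The cost is some cohort programming and fewer pre-policy person-years.

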**Table 1. Proposed Outcomes for the Pre-diabetes and Diabetes Cohorts**

Outcomes	Definition	Notes
Pre-diabetes cohort		
Weight loss during counseling	Weight lost from first IBT visit to final IBT visit	Available at all PaTH sites
Weight loss maintenance	% of weight lost during program and maintained over remaining time period, reported by year	Available at all PaTH sites
Diabetes incidence	% of patients who develop diabetes per year following weight counseling	Available at all PaTH sites
Patient-reported outcomes	-SF-12 -PHQ-2, PHQ-8, PHQ-9 -Physical function -sleep -fruit and vegetable consumption -social support -physical activity -PROMIS (PROMIS 29, physical function, depression) -healthy lifestyles -patient reported medication reconciliation	Available at some sites – Formal inventory of PROs will be collected at each institution at the beginning of the project, to be included as secondary outcomes
Diabetes cohort		
Weight loss during counseling	Weight lost from first IBT visit to final IBT visit	Available at all PaTH sites
Weight loss maintenance	% of weight lost during program and maintained over remaining time period, reported by year	Available at all PaTH sites
Patient reported outcomes	-SF-12 -PHQ-2, PHQ-8, PHQ-9 -Physical function -sleep -fruit and vegetable consumption -social support -physical activity -PROMIS (PROMIS 29, physical function, depression) -healthy lifestyles -patient reported medication reconciliation	Available at some sites – Formal inventory of PROs will be collected at each institution at the beginning of the project, to be included as secondary outcomes
Uncontrolled diabetes	Average A1c > 9 or no A1c	Available at all PaTH sites
Controlled blood pressure	SBP < 140, DBP < 90, averaged across values over year	Available at all PaTH sites
On a statin medication	Evidence of a statin medication on current EHR medication list	Available at all PaTH sites
Receiving annual eye exam	Documentation of eye exam once in past year	Available at all PaTH sites
Receiving annual urinary microalbumin test	Documentation of lab testing for urinary microalbumin at least once in past year	Available at all PaTH sites
Lower extremity amputations	Documentation of procedure for lower extremity amputation or billing code through health plans in past year	Available at all PaTH sites

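### The code route for type 2 diabetes names only ICD-9 250.xx for a cohort followed to 2019: it does not separate diabetes types, and it would miss code-only cases after any change of ICD version

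*Combined protocol and SAP*

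**What the plan says.** Section 7.2 (Diabetes Cohort Definition) classifies a patient as having type 2 diabetes by any one of four routes. Three are "type 2 diabetes mellitus on the problem list, diabetes-specific medications, hemoglobin A1c (HbA1c) results > 7.0" (per cent). The fourth is "one inpatient diagnosis code or two outpatient diagnosis codes for type 2 diabetes (ICD-9 codes 250.xx"). Section 3.1 repeats the code rule: "one inpatient diagnosis code or two out-patient diagnosis codes for type 2 diabetes (ICD-9 codes 250.xx"). Section 4.2 bases the computable phenotypes on these criteria, and the only exclusion in section 3.2 is age under 18.

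The opening of section 7.2 uses the same code range without a type. The network's diabetes count is "defined as age 18 and older with a diagnosis of diabetes mellitus – ICD9 250.xx".

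The cohort is open, "with new patients added into the cohort after 2015 as they meet the diabetes cohort definition prospectively", and "The observational period for the outcome variables will be for the 10-year period from 2009-2019". The extraction used for cohort validation covers 2009-2015.

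Diabetes incidence is an outcome in both aims (section 1.0). Table 1 describes it as the percentage "of patients who develop diabetes per year following weight counseling" and gives no case definition.

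**The concern.** Two separate weaknesses follow from this one rule.

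**Type.** Section 7.2 lets 250.xx stand for diabetes mellitus in general and, a paragraph later, for type 2. No subcode is excluded. Programmed literally, the code route admits patients who do not have type 2 diabetes.

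**Version.** The rule is tied to one ICD version for the whole of 2009-2019. If coding moves to another version in that window, one of the four routes stops finding new cases. Section 8.0 models the outcome with a single change of slope at the policy date and no term for a later break. A loss of capture inside the post-policy segment would therefore be absorbed by the post-policy slope, and section 8.0 reads a change in that slope as possible evidence of policy impact. Lost cases look like falling incidence, which is the direction of benefit. Validation on 2009-2015 data would largely miss a break near the end of that period and would wholly miss a later one.

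**Working it through.** **1. The plan's own figure.** The five site counts in section 7.2 sum to 25,219 + 150,589 + 60,324 + 40,536 + 51,787 = 328,455, which matches the stated total. This is a count of any 250.xx diabetes, not of patients meeting the type 2 algorithm. It is evidently the basis of the figure of more than 320,000 in the power paragraph.

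**2. Type.** The documents do not give the share of 250.xx patients who do not have type 2 diabetes. Assumed shares, with counts rounded:

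| Assumed non-type-2 share | Not type 2 | Remaining |
|---|---|---|
| 2% | 6,569 | 321,886 |
| 5% | 16,423 | 312,032 |
| 10% | 32,846 | 295,610 |

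This applies in every year the range is used, pre-policy years included.

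**3. Version: loss of capture.** Let *f* be the share of new cases that qualify by code alone and would never qualify by problem list, medication or HbA1c. If ICD-9 codes stop being recorded, recorded incidence = true incidence × (1 − *f*). The documents do not give *f*. For an assumed range of 5% to 50%, the factor runs from 1 − 0.05 = 0.95 to 1 − 0.50 = 0.50.

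**4. Version: effect on the segmented model.** The section 8.0 form is

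- logit μ = β0 + (t + 5)β1 for t ≤ 0
- logit μ = β0 + 5β1 + tβ2 for t ≥ 0

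Inputs from the plan: years 2009-2019, and time origin 2014 (stated for Utah), so t = −5 to 5. Assumed inputs: true incidence flat at 1% per year; ICD-9 coding ends in late 2015, so a quarter of 2015 and all of 2016-2019 are affected; 200,000 patients per year; no clustering.

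At *f* = 10%, for example, recorded incidence is 1.000% for 2009-2014, 1% × (1 − 0.10 × 0.25) = 0.975% for 2015, and 1% × (1 − 0.10) = 0.900% for 2016-2019. The fixed-effects version of the model, fitted to such series, gives:

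| *f* | Annual OR, pre | Annual OR, post | Post/pre ratio | z for slope change |
|---|---|---|---|---|
| 5% | 0.998 | 0.988 | 0.990 | −1.2 |
| 10% | 0.997 | 0.976 | 0.979 | −2.4 |
| 20% | 0.994 | 0.949 | 0.955 | −5.2 |
| 30% | 0.991 | 0.919 | 0.927 | −8.4 |
| 50% | 0.988 | 0.842 | 0.853 | −16.5 |

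The true ratio is 1 throughout. Section 2.1 dates the coverage changes to 2012 and 2013. Those origins give similar ratios: 0.988 and 0.989 at *f* = 5%, 0.848 and 0.853 at 50%. Doubling the incidence to 2% leaves the 2014-origin ratios at 0.990 and 0.852. The z values depend on the assumed 200,000 per year and would shrink once clustering is allowed for.

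**The case against.** **Codes are one of four alternatives.** This stands, and it limits the effect. Only code-only patients are lost. A patient first found by code who later qualifies by medication, problem list or HbA1c is delayed, not lost, so a first-found share would overstate *f*. At *f* = 5% the false slope change is about 1% per year and would be hard to see even under the favourable assumptions above.

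**No ICD change is mentioned in the documents.** True. The version point is conditional on one, and its date is also assumed.

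**The section 7.2 total is a feasibility count, and the operative rule says type 2 before the bracket.** The bracket can be read as a code family limited by those words. That reading is possible, but no subcode is named to carry it out. Excluding subcodes would also not fully settle case mix, because the medication and HbA1c routes do not separate types either.

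**Incidence may not use this algorithm.** Table 1 does not say. Section 4.2 makes the algorithm the natural choice, and no other is given. The bias matters for the Aim 1 pre/post comparison. In the post-policy analysis by number of visits, a calendar-time loss would affect patients at every visit level and need not look like a policy effect.

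**Validation and data checks are planned.** Sections 4.2, 7.2 and 13.5 provide for them, but none names a coding transition, and the validation extract ends in 2015.

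A reader might infer that post-policy incidence and case mix are already known to be distorted. The documents do not support that: the version change and the code-only share are both unknown. Nor does the type overlap create a post-policy break by itself, since it runs through all years; case mix would shift over time only if the balance of routes changed.

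**Conclusion.** The point holds as a specification defect with a conditional bias.

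Established from the text: the code route names only ICD-9 250.xx for a cohort that accrues after 2015 and is followed to 2019; the same range is used for diabetes of any type; and no later code set or exclusion of other types appears.

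Conditional: if sites change ICD version in the window and incidence uses the cohort algorithm, recorded incidence afterwards is 1 − *f* of the true value, or 0.95 to 0.50 for an assumed *f* of 5% to 50%. The segmented model then shows a false post/pre ratio of annual odds ratios of about 0.99 to 0.85, toward apparent benefit. The lower end is small. From about *f* = 10% the artefact could reach nominal significance at the assumed sample size, and the power paragraph itself expects very small effects to be detectable. The likely value of *f* cannot be derived from the documents.

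This should be corrected before the final extraction. It is not a reason to doubt the design as a whole.

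**What to change.** - In sections 3.1 and 7.2, replace 250.xx with a list of type 2 codes for every ICD version in use during 2009-2019, with non-type-2 subcodes excluded.
- In Table 1, state that incident diabetes uses this algorithm.
- Tabulate or plot new cases by route (problem list, medication, HbA1c, code) across any version change. If a break is seen, add a version indicator to the incidence model as a sensitivity analysis.

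The cost is a code list and one plot. The downside is a diabetes count that may fall somewhat below the any-type figure of 328,455, which would need restating in section 7.2 and the power paragraph.
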